### 6.1. Table of Exam 7 Components by Core or Ancillary Study

A brief summary of the funded Exam 7 Core and Ancillary Studies Components is provided below in Table 4. All six Field Centers are included in all ancillary studies. All participants are selected for all ancillary studies unless they meet study-specific exclusion criteria.

**Table 4: Exam 7 Components**

Title	PI	Components (time)	Total Time	Blood draw/ volume	Radiation
Core	[name]	Consent/Check-in (20m) Seated Blood Pressure (12m) Anthropometry (10m) Phlebotomy/Urine (15m) Medical History (5m) Personal History/Demographics (10m) Medications Inventory (10m)	90 min	70 mL total includes core and all Ancillary Studies.	none
MESA-MIND	[name]	Consent (Core) Informant info (2 min) Anthro, blood pressure (Core) Blood draw (Core) Arterial stiffness (20min) Meds, MedHx (Core) UDS physical exam and SPPB (30 min) Cognitive testing (60 min) Brain MRI (60 min) Brain amyloid PET (120min) Informant interview (no ppt burden)	250 min for all 340 with amyloid PET	26 mL (part of 70 mL total)	3.46 mSv for PiB or 0.646 rem for Florbetaben in up to 600 participants (JHU/COL/WFU)
MESA 24-H ACT Study	[name] [name] [name]	Consent (Core) Phlebotomy (Core) Activity monitor (hip) (8 days during all waking hours) Sleep monitor (wrist) (8 days during all sleeping hours, or 24 hours)	30 minutes in clinic 30 minutes at home (includes ~3-4 minutes/day to put on/take off activity monitor and fill out wear/sleep and nap logs)	7 ml (from MIND, part of 70 mL total)	none

Title	PI	Components (time)	Total Time	Blood draw/ volume	Radiation
		Daily wear, sleep, and nap logs (20 min of instruction time).			
MESA Glucose Homeostasis	[name]	Consent (Core) Monitor instructions and application (25 min, wear 7-14 days) At home diary 2 years later (n=1000): Repeated monitor/diary/cognitive testing	25 minutes in clinic 210 minutes at home 2 years later: 210 minutes at home 30 minutes at home for abbreviated remote cognitive testing (only if MESA-MIND is not renewed)	3ml (part of 70mL total)	none
MESA Neighborhood III	[name]	Consent (Core) Questionnaire (25 min)	25 minutes	none	none
MESA Sleep	[name]; [name]	Consent (Core) Home visit consisting of overnight sleep study (polysomnography) and sleep monitor (wrist) for 8 days Questionnaire (125 min) Neck measurement 24 hour ambulatory BP monitor At home sleep diary	5 minutes in clinic 90 minutes at home for initial home visit (includes PSG setup, BP cuff measurement, monitor use instructions, and questionnaires) 24 hours PSG (concurrent with first day of wrist sleep monitor) 24 hours activity monitor (hip) for 8 days 24 hours ABPM (concurrent with last day of wrist sleep monitor)	none	none

Title	PI	Components (time)	Total Time	Blood draw/ volume	Radiation
MESA Lung IV	[name]	Consent (Core) Blood and urine (Core) Environmental Exposures Questionnaire (15 min) Spirometry exclusion/completion (5 min) Pre-bronchodilatory spirometry (15 min) Post-bronchodilator spirometry (5 min) Pulse oximetry (Core) Non-contrast Lung CT (30 min) Nasal brushing (5 min, N=1000, select all) Hair collection(10 min, N=1350, select all) PAXgene tube (n=300)	86 min	2.5 ml (part of 70 mL total)	3 mSv
MESA Stress Reactivity	[name]	Consent (Core) Heart Monitor Patch Application/Instructions (30 minutes, 7 days wear time) Daily Stress Questionnaire (15 minutes for 7 days)	30 min in clinic plus 15 min daily for 7 days	none	n/a

## 6.2. Description of Exam 7 Components by Core or Ancillary Study

### 6.2.1. Core Exam Components

- **Blood Pressure:** Resting blood pressure will be measured preferably in the right arm after five minutes in the seated position. An automated oscillometric method (Dinamap) and appropriate cuff size will be used in clinic. Three readings will be taken; the second and third readings will be averaged to obtain the blood pressure levels used in analyses. Home visits will use a mobile blood pressure device (OMRON 10).
- **Anthropometry:** Height and weight will be measured to the nearest 0.1 cm and 0.5 kg respectively. Body mass index (kg/m^2) will be used as a measure of overall obesity. Girths (neck, waist at the umbilicus and hips at the maximal circumference of buttocks) will be measured to the nearest 0.1 cm using a steel measuring tape (standard 4 oz. tension).
- **Pulse Oximetry:** Resting oxygen saturation will be measured in the seated position using a pulse oximeter with a finger probe. Nail polish will be removed if necessary. Oximetry will be measured off supplemental oxygen if used. For participants who use supplemental oxygen, supplemental oxygen will be restarted immediately if they are short of breath or their oxygen saturation drops below 82%.
- **Laboratory Measurements:** A maximum of 70mL of blood and spot urine will be collected (which includes all core and ancillary studies). Core measurements will include a lipid profile, glucose, creatinine, insulin, HbA1C, and urinary creatinine and albumin. White cells may also be cryo-preserved for future generation of cell-lines and isolation of DNA needed for genetic studies. If samples are lost or damaged, participants will be invited to repeat the biosample collection on a different day.
- **Questionnaires:** Standard questionnaires (similar to those at prior MESA exams) will be used to collect information about demographics, socioeconomic and psychosocial status, physical function, medical, ~~and~~ family, ~~and~~ sleep history, medication use, dietary and alcohol intake, and smoking.

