- **Ambulatory Blood Pressure Monitoring:** The 24-hour ambulatory blood pressure monitoring can be uncomfortable because of the repetitive inflation of the blood pressure cuff. Participants may feel discomfort from the blood pressure cuff on their arm when it inflates. During sleep, the cuff may cause sleep disruption. Very rarely, the pressure may damage a nerve in the arm.
- **The following procedures were assessed and do not have any foreseeable risk to participants, beyond the risks of loss confidentiality in the event of a data breach:**
  - **Seated blood pressure**
  - **Anthropometry**
  - **Urine collection**
  - **Collection of personal history/medical history/medications and other questionnaires.**
  - **Completion of home diaries and non-sensitive questionnaires**
  - **Neck measurement**
  - **Pulse oximetry**

Participation in research carries a theoretical risk for some people of being given information that they might prefer not to have heard (for example, some test results) or that may be difficult for them or their health care provider to interpret. This may lead to other tests, which MESA will not pay for.

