**Table 5: Exam Components allowed by each visit type**

[figure not shown]
Component	Study	Visit Type			
		In-clinic	Home	Remote	Phone
Clinic Reception and Consent	All	Yes	Yes	Yes	No
Blood Pressures	Core, MIND	Yes	Yes	No	No
Pulse Oximetry	Core, Lung	Yes	Yes	No	No
Height	Core, MIND	Yes	Yes	No	No
Weight	Core, MIND	Yes	Yes	No	No
Waist circumference	Core, MIND	Yes	Yes	No	No
Neck circumference	MIND, 24hAct	Yes	Yes	No	No
Phlebotomy	Core, 24hAct, Glucose, Lung, MIND	Yes	Yes	No	No
Urine Collection	Core/Lung	Yes	No	No	No
Medications	Core, MIND	Yes	Yes	Yes	No
Medical History	Core, MIND	Yes	Yes	Yes	Yes
Personal History/Demographics	Core	Yes	Yes	Yes	Yes
Arterial Stiffness	MESA-MIND	Yes	No	No	No
Clinician’s Physical Examination		Yes	No	No	No
SPPB		Yes	No	No	No
Cognitive Testing		Yes	Yes	Yes	No
Brain MRI		Yes	No	No	No
PET imaging		Yes	No	No	No
Informant Interview		Yes	Yes	Yes	No
Sleep Questionnaires	MESA Sleep	Yes	Yes	Yes	Yes
Sleep Study/Diary		No	Yes	Yes	No
Actigraphy/Diary		Yes	Yes	Yes	No
Blood Pressure Monitor/Diary		Yes	Yes	Yes	No
Activity and Sleep monitor/Diary	24hACT	Yes	Yes	Yes	No
Physical Activity Questionnaire		Yes	Yes	Yes	Yes
Spirometry exclusion/completion	Lung IV	Yes	Yes	No	No
Pre and post-bronchodilatory spirometry		Yes	Yes (no BD)	No	No
Environmental Exposures Questionnaire		Yes	Yes	Yes	Yes
Nasal brushing		Yes	No	No	No
Hair collection		Yes	No	No	No
Lung CT		Yes	No	No	No

Neighborhood Questionnaire	Neighborhood	Yes	Yes	Yes	Yes
Continuous Glucose Monitor/Diary	Glucose	Yes	Yes	Yes	No
Cardea SOLO Patch	Stress Reactivity	Yes	Yes	Yes	No
Daily Stress Questionnaire		Yes	Yes	Yes	No

Examples of the different exam models are reflected in the next sections. The order of exam components remains flexible based on the priorities of the study and the needs of the participants.

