### 12.2.1. Coordinating Center

- Establish a study timeline to guide overall study activities, including planning and oversight of Steering Committee and subcommittee activities.
- Provide leadership and coordination for establishing and maintaining study communications, including the use of video conferencing, meetings, and a central, accessible website.
- Provide administrative leadership and scientific coordination to develop the final study protocol, manuals of operations, and forms, including sample selection, recruitment, certification of field staff, examination, interview, medical record abstraction, and follow-up procedures.
- Develop, implement and maintain a database management system capable of: storage of existing participant data; data entry and weekly transmittal at each of the Field Centers, Reading Centers and Laboratories; generation of reports for use by Field Centers, Project Office and Steering Committee; and summaries of exam to be sent to participants and their physicians.
- Coordinate training and certify Field Center staff in examination procedures and interviews in accordance with protocol.
- Purchase, distribute, and coordinate utilization of appropriate common mechanical and electronic equipment among all centers, including computer hardware and software.
- Develop and maintain manuals of operations describing in detail study activities at each participating center.
- Develop, implement and maintain a system for quality control of data to verify completeness, compare the distribution of values from different Field Centers and different examiners, identify outlying values for separate review, review adherence to schedules for reexaminations and other data collection and analyze laboratory performance on external standards and blind duplicates.
- Provide leadership for the editing, analysis, and publication of study data in collaboration with the Steering Committee and the NHLBI Project Office.
- Provide support for Monitoring Board meetings.
- Produce data sets of MESA data for use by investigators and for distribution to the public, according to NHLBI guidelines.

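### Section 4.2.2 lists pulse oximetry as free of foreseeable risk, while section 6.2.1 takes oxygen users off oxygen for it and foresees breathlessness or desaturation

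*Protocol*

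**What the plan says.** Section 6.2.1 of the protocol (Core Exam Components) defines the measurement: "Resting oxygen saturation will be measured in the seated position using a pulse oximeter with a finger probe". For oxygen users it adds a condition: "Oximetry will be measured off supplemental oxygen if used". It then gives a safeguard: "supplemental oxygen will be restarted immediately if they are short of breath or their oxygen saturation drops below 82" per cent.

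Section 4.2.2 (Physical and Emotional Risks) goes through the exam procedures one by one. It ends with a list of procedures that, in its words, "do not have any foreseeable risk to participants, beyond the risks of loss confidentiality in the event of a data breach". One entry in that list reads simply "Pulse oximetry". There is no footnote or exception for participants who use oxygen, and no other entry in section 4.2.2 mentions removing it.

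Table 5 shows where the procedure may take place: "Pulse Oximetry Core, Lung Yes Yes No No". The columns are in-clinic, home, remote and phone, so oximetry is allowed in clinic and at home.

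**The concern.** For most participants, oximetry is a finger probe and nothing more, and a no-risk entry is unremarkable. For a participant on supplemental oxygen, section 6.2.1 makes it something else: a treatment is interrupted for a research reading, and the protocol says what is to happen if the participant becomes breathless or desaturates. The risk section then states that the procedure carries no foreseeable risk.

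What is at stake is the accuracy of the safety information. Section 4.1 has investigators and staff go through risks and benefits and adapt that discussion to the individual. For an oxygen user, section 4.2.2 gives them nothing to adapt, and what it does say points the wrong way. Section 3.5 puts the average age of active participants at 78.5 years (October 2021). Table 4 lists oximetry under MESA Lung, whose subject is emphysema and chronic obstructive lung disease. Oxygen users in this cohort are therefore plausible, and section 6.2.1 itself provides for them.

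**Working it through.** No arithmetic applies. The only figure is the 82 per cent threshold. It appears once and no second value contradicts it. The check is a comparison of texts.

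1. **What is done.** Section 6.2.1 removes oxygen from participants who use it, for the purpose of the reading. Removal is written into the pulse oximetry item itself, so for these participants it is part of the procedure.

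2. **What is foreseen.** The same item gives two triggers for restarting oxygen: shortness of breath, and saturation falling below the stated level. A rule that acts on an event presupposes that the event can be foreseen. It need not be likely.

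3. **What the risk section says.** Section 4.2.2 names pulse oximetry as a procedure that was assessed and found to have no foreseeable risk except loss of confidentiality. The statement is unqualified.

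4. **Whether the risk is described elsewhere in section 4.2.2.** It is not. The entries cover blood draw, arterial stiffness, spirometry, lung CT, the heart rhythm patch, brain MRI, the physical performance battery, cognitive testing, amyloid PET, the sleep study, the wearable monitors, glucose monitoring and ambulatory blood pressure. None mentions interruption of oxygen.

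5. **What standard the section applies to other procedures.** The bar for naming a risk is low. Section 4.2.2 mentions skin irritation from a wrist band, cough or dizziness from spirometry, and boredom from cognitive tests. For the physical performance battery it names breathlessness, while calling the risks of that test rare. The same symptom is a restart trigger in section 6.2.1, yet oximetry is placed among the procedures without risk.

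Steps 2 and 3 contradict each other for oxygen users. Step 4 shows that the gap is not filled elsewhere in the section. Step 5 shows that the omission does not follow from a policy of leaving out minor or rare effects.

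**The case against.** The strongest defence is that section 4.2.2 means the finger probe, which is harmless, and that section 6.2.1 merely adds a precaution for a subgroup. The list makes no such distinction, however, and section 6.2.1 puts the removal of oxygen inside the procedure. What stands is that the entry is accurate for participants who do not use oxygen, so the repair is small.

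A second defence is that the single IRB reviews the whole protocol (section 4.1), so the restart rule was before it. That is fair. It would be wrong to say that the step was hidden from the IRB. It remains true that the section meant to set out risks contradicts the section describing the procedure. What the consent form says cannot be judged, because it was not available.

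A reader might also infer a data problem: that readings ended by the restart rule are truncated near the threshold, lost or mixed with completed ones, and that an endpoint is biased as a result. The protocol does not support this. The rule says when oxygen is restarted. It does not say that the value is capped, discarded or pooled. No recording duration is given, so the protocol does not define a completed or an early-stopped reading. Oximetry is not named as an endpoint in the Exam 7 aims (section 2) or the MESA Lung aims (section 5.6). Recording detail may properly sit in the manuals, since section 12.2.1 charges the Coordinating Center to "Develop and maintain manuals of operations describing in detail study activities at each participating center", or in forms or an analysis plan that are not at hand. The absence of a stated time off oxygen is silence of the same kind, and is not counted here as an error.

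**Conclusion.** The point holds as an internal contradiction. For participants who use supplemental oxygen, the no-foreseeable-risk statement in section 4.2.2 is wrong as written, because section 6.2.1 foresees breathlessness or desaturation during the same procedure. The two sections must be reconciled.

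Its reach is limited to oxygen users examined in clinic or at home. The protocol gives neither their number nor how many would meet a restart trigger, so no count is offered. No sample size, analysis or estimate changes. The correction is worth making because it concerns safety information for a frail subgroup and costs almost nothing.

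The conclusion rests on one reading: that a procedure includes the steps its own protocol item prescribes. It does not depend on whether the threshold is suitable, and none of this is a view on the threshold or on how oxygen should be managed.

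**What to change.** Reconcile sections 4.2.2 and 6.2.1:

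- In section 4.2.2, limit the no-risk entry for pulse oximetry so that it no longer covers oximetry off oxygen in participants who use it.
- In the same section, add a short entry describing the interruption of oxygen for the measurement and the effects that section 6.2.1 already foresees.
- Check that the consent text agrees with the revised section, and amend it only if it does not.

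The clinical content of the restart rule stays with the sponsor and the investigators. The cost is a few lines of wording in one section and a check of the consent form, submitted to the single IRB as a protocol change. No procedure, visit or data item is added.

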### 6.2.2. MESA-MIND Exam Components

- **Additional Blood Collection:** A total of 26 mL will be collected for future assay of established and evolving AD biomarkers. The 26 mL of blood will be used to add novel biomarkers from plasma exosomes and pericyte function. This is included in the maximum blood draw volume of 70 mL.
- **Arterial Stiffness Measures:** Assessment of arterial pulse waves and pulse wave velocity will be performed using a brachial and leg cuff-based approach (with a simultaneous, automated recording of the cuff blood pressure) using a Fukuda VaSera.
- **Cognitive Function Testing:** Cognitive tests administered at MESA Exam 5 and repeated for Exam 6 and MESA-MIND Visit A (2019-2021) - which included the Cognitive Abilities Screening Instrument (CASI), Digit Symbol Coding (DSC), and the Digit Span Test (DST) – will be repeated again in 2022-23 for MESA Exam 7 (2022-2023). The reassessment will allow for examination of cognitive trajectory and whether cardiometabolomic and AD biomarkers predict incident MCI and dementia. The

measures will be supplemented by the standardized set of measures (Uniform Data Set; UDS version 3) that are collected nationally and longitudinally by all Alzheimer's Disease Centers to characterize mild AD, MCI and vascular dementia. The UDS includes the following tests: Montreal Cognitive Assessment (MoCA: a brief test of global cognitive function that assesses attention, working memory, short-term memory, language, and visuospatial ability), Story Recall (participants hear a short story and are asked to recall the details immediately after it is read and again 20 minutes later), Benson Complex Figure Test (participants view a complex figure and are asked to draw the figure from memory immediately after exposure and again 20 minutes later), Verbal Fluency (participants list as many words as possible in 60 seconds that begin with a particular letter of the alphabet or that belong to a particular category, such as "animals"), and a clinician-administered physical exam. Frequent breaks will be provided as needed, and participants will be informed that testing can be discontinued at their request. All cognitive assessments will be administered by trained, certified staff under the supervision of ancillary study investigators. Cognitive test administration will be audio-recorded for random quality control checks to correct drift. Participants may complete cognitive assessments in-person, by video call, or by telephone (if in-clinic or video assessments are not possible). Participants with clinical or research diagnosed dementia will not have cognitive function testing.

- **Clinician's Physical Examination:** A clinical neurological exam will be administered by a trained nurse, nurse practitioner, physician's assistant, clinical fellow, a coordinator with medical training, or medical doctor. It will assess basic neurological signs and symptoms of stroke and Parkinsonism.
- **Short Physical Performance Battery (SPPB):** The SPPB is a group of measures that combines the results of gait speed, chair stand, and balance tests in order to assess the lower extremity functioning in older persons.
- **Brain MRI:** MRI data will be acquired in accordance with multisite protocols including ADNI2, and the NINDS Common Data Elements recommendations. All images will be acquired on a 3T Siemens scanners with a high resolution 20-channel head/neck coil. Sequences include: T1 and T2 (for morphology), T2 FLAIR (to quantify white matter hyperintensities), DTI (to assess microstructural integrity of the white matter), BOLD/fMRI (for resting state brain connectivity), pseudo-continuous arterial spin labeling (pcASL, for quantification of cerebral blood flow), and susceptibility-weighted Images (SWI). The brain MRI protocol is consistent with the Atrial Fibrillation Study MRI protocol.
- **Amyloid PET Imaging:** The subset of study participants at Wake Forest, Columbia and Johns Hopkins Field Centers who agree to participate in the optional CT/PET scans will receive amyloid imaging with low-dose CT for attenuation correction. Fields Centers will use either the [11C] Pittsburgh Compound B (PiB) or [18F] Florbetaben (Neuroceq®) PET tracer. The total radiation exposure of the PET scan with PiB is approximately 0.347 rems, which includes exposure associated with the head CT completed prior to the PET. For Florbetaben, total radiation exposure is approximately 0.646 rem. Participants will be monitored from the time of tracer injection until after the imaging session is complete for

signs of rare adverse events. Participants who receive the PiB tracer will also be contacted 24-72 hours after the procedure by telephone to inquire about adverse events. Participants with clinical or research diagnosed dementia will not have amyloid PET imaging.

### 6.2.3. MESA 24H-ACT Exam Components

- **Sleep Monitoring:** A wrist sleep actigraphy device (GeneActiv) will be used to determine sleep duration and quality. Participant instruction and distribution of the wearable devices will occur at the end of the participant's MESA Exam 7 visit, at a home or remote visit. Participants will receive verbal or written instructions and a package that includes the wrist sleep monitor, detailed written wear instructions, a tracking log, and contact information. The monitor will be programmed and standardized by staff at the clinic prior to distribution and initializing data recording. The wrist sleep monitor will be worn for the entire 24-hour period and simultaneously with the activity monitor (described below) for the duration of 8 days. Three days after receiving the device, study staff will call to confirm device wear, address any questions, and trouble-shoot problems. Participants will return the device and related materials to study staff using a pre-paid and addressed envelope or provide it to study technicians at a home visit after 8 days on the wrist during all sleeping hours. Participants may be asked to repeat the sleep monitoring if it captures less than 5 days of data or if another scientific question arises that could be answered with repeated activity monitoring.
- **Activity Monitoring:** The ActiGraph wGT3X-BT activity monitor (ActiGraph, Pensacola, FL) will be used to detect waking behaviors. Participant instruction and distribution of the hip activity monitor will also occur at the end of the participant's MESA Exam 7 visit (or provided at a home visit or mail), along with the wrist sleep monitor. The device would similarly need to be initialized to begin data collection by staff at the clinic using ActiLife6 software prior to device distribution. The hip activity monitor will be worn simultaneously with the wrist sleep monitor (described above) for the duration of the 8 days. Three days after receiving both devices, study staff will call to confirm device wear, address any questions, and trouble-shoot problems. Participants will return the device and related materials to study staff using a pre-paid and addressed envelope or provide it to study technicians at a home visit after 8 days on the hip during all waking hours. Upon receipt of the hip activity monitor, study technicians will download the data using ActiLife6 software and fully charge the battery prior to distributing the device to a new participant. Participants may be asked to repeat the activity monitoring if it captures less than 5 days of data or if another scientific question arises that could be answered with repeated activity monitoring.
- **Sleep and Nap Tracking, including Prompts for Daily Wear:** Each day in the tracking log, participants will take 3-4 minutes to record the times corresponding to when the wrist sleep monitor was replaced with the ActiGraph (waking periods), and when the hip activity monitor was replaced with the wrist sleep monitor (sleep periods). Participants will also record the clock-times corresponding to when s/he took any naps during waking

periods. This log will be integrated into the diaries used by other ancillary studies with wearables.

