#### 6.2.6. MESA Sleep Exam Components

- **Sleep Actigraphy Monitoring (Wrist):** Participants will be fitted for a wrist sleep monitor during the Exam 7 clinic visit or home visit, or mailed the device and given telephone instructions. Devices will be programmed before distribution. The wrist sleep monitor device (GeneActiv) will be worn on the nondominant wrist for 8 consecutive days to improve rhythm assessment and to overlap, as possible, both the night of the polysomnography study and 24-hour ABPM (ambulatory BP). The device looks like a wristwatch, has a patient-activated event marker, a rechargeable battery, and light sensor. These features improve the ability to annotate off times and sleep onset/offset and provide high quality light data to allow analysis of light cues in relationship to sleep-wake patterns. The device can be worn during showering and bathing but should be removed during prolonged periods of immersion (swimming). Instructions on returning the device with use of a pre-paid mailer will be provided (unless retrieved at the time of a study technician home visit). Once the watch is returned to the Field Center, a staff member will download the data using commercial software and electronically transfer the data files to the Sleep Reading Center (SRC) via a secure website. Sleep diaries will be concurrently scanned and sent to Brigham and Women's Hospital to be used when editing each record. Participants may be asked to repeat the sleep monitoring if it captures less than 5 days of data or if another scientific question arises that could be answered with repeated activity monitoring.
- **Sleep Diary Entry:** Participants will be instructed on completing a brief daily sleep log for 8 consecutive days (while using the wrist sleep monitor), when waking up daily, recording bed & wake-up times, recording perceived sleep latency, naps, any unusual events during the day or night, ratings of sleep quality, times when the wrist sleep monitor and BP cuff (first night only) is removed. This information will be used to edit the wrist sleep monitor data, provide subjective reports of daily variation in sleep patterns and identify factors that influence night-to-night variability. This diary will be integrated into the logs used by other ancillary studies with wearables.

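### The protocol gives incompatible wear times for the shared wrist monitor; sleep-only wear would remove the waking data that MESA Sleep's rhythm and light measures need

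*Protocol*

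**What the plan says.** Wear time is stated in several places in the Protocol.

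- **6.2.3, Sleep Monitoring, main instruction:** "The wrist sleep monitor will be worn for the entire 24-hour period and simultaneously with the activity monitor", for eight days.
- **6.2.3, Sleep Monitoring, sentence on returning the device:** return comes "after 8 days on the wrist during all sleeping hours".
- **6.2.3, Activity Monitoring:** "The hip activity monitor will be worn simultaneously with the wrist sleep monitor (described above) for the duration of the 8 days". The return sentence there limits the hip device to waking time: "after 8 days on the hip during all waking hours".
- **6.2.3, Sleep and Nap Tracking:** each day participants are to "record the times corresponding to when the wrist sleep monitor was replaced with the ActiGraph (waking periods"), and to record the reverse exchange for sleep.
- **Table 4, 24-H ACT row:** "Sleep monitor (wrist) (8 days during all sleeping hours, or 24 hours"). The hip monitor in that row is for waking hours.
- **Table 4, MESA Sleep row, total-time column:** "24 hours activity monitor (hip) for 8 days". The component column of the same row lists a wrist monitor, not a hip monitor.
- **6.2.6, Sleep Actigraphy Monitoring:** the same wrist device model is worn for "8 consecutive days to improve rhythm assessment". This section also relies on the device's light sensor, lets it stay on for showering and bathing, and has it taken off only for prolonged immersion.

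Section 5.5 makes quantitative circadian metrics an output of MESA Sleep. Section 5.2 builds the 24-hour activity cycle from the hip monitor and sleep actigraphy together.

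**The concern.** Simultaneous wear and exchange of the two devices cannot both be followed. A participant who keeps the wrist monitor on all day supplies movement and light data across the full cycle. A participant who exchanges devices supplies wrist data for sleep only. Rest-activity rhythm and daytime light exposure need the waking part of the record, so the second participant cannot contribute these measures to MESA Sleep.

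The conflict reaches MESA Sleep because the wrist device model is common to both studies, Section 6.1 selects all participants for all ancillary studies unless excluded, and the 24H-ACT log is merged into the diaries of the other wearable studies. The log's own title says that it includes prompts for daily wear, so its wording can shape behavior. In the remote option (6.3.3) devices are mailed and applied under telephone or video guidance, so written material carries more weight. Daytime data missed in this way can be recovered only by repeating the monitoring.

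**Working it through.** The protocol states no figure to reproduce. The check compares the wear patterns and then does simple arithmetic on hours.

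**Step 1. What each statement implies for waking hours**

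| Place | Wrist monitor while awake | Hip monitor while awake | Both worn together? |
|---|---|---|---|
| 6.2.3, main wrist instruction | on | on | yes |
| 6.2.3, wrist return sentence | off | not stated | no |
| 6.2.3, hip instruction | on (simultaneous) | on | yes |
| 6.2.3, tracking log | off (exchanged) | on | no |
| Table 4, 24-H ACT | on or off | on | either |
| 6.2.6, MESA Sleep | on (implied by rhythm and light purpose) | not mentioned | not applicable |

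The hip monitor is limited to waking hours under 24H-ACT, so the instruction to wear the devices simultaneously can only refer to waking hours. In a true exchange, the overlap in those hours is zero.

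**Step 2. Size of the loss under sleep-only wear**

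Inputs: 8 days (6.2.3 and 6.2.6) and sleep of *s* hours per day. The protocol does not give *s*; I assume 6, 8 and 9.

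- Full wear: 8 × 24 = 192 wrist hours.
- Sleep-only wear: 8 × *s* hours. Share missing: (24 − *s*)/24.

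| *s* | Wrist hours recorded | Share recorded | Share missing |
|---|---|---|---|
| 6 | 48 | 25% | 75% |
| 8 | 64 | 33.3% | 66.7% |
| 9 | 72 | 37.5% | 62.5% |

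The missing part is the whole waking period whatever *s* is, so the conclusion does not depend on the exact value.

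**Step 3. What an exchange leaves intact**

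Hip coverage is (24 − *s*) hours and wrist coverage is *s* hours, which sum to 24. In 6.2.3 the hip device measures waking behavior and the wrist device measures sleep. The 24H-ACT composite of sedentary time, light activity, moderate-vigorous activity and sleep can therefore still be assembled, apart from gaps at changeover.

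**Step 4. Would the safeguards catch it?**

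The repeat rule in 6.2.3 and 6.2.6 is triggered by fewer than five days of data and names no minimum hours per day. Eight sleep-only days are eight days of data. The call on day 3 confirms wear, but with two patterns in the text it has no single standard to check against.

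**Step 5. Which reading fits the rest of the protocol**

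The main wrist instruction, the rhythm and light purpose in 6.2.6, and the permission to bathe with the device all point to continuous wrist wear. So does Table 4's 24-H ACT burden entry, which counts daily time for putting on and taking off the activity monitor only.

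**The case against.** The best defense is that the main instruction is clear and the rest is loose drafting. The sleeping-hours wording sits in a sentence about returning the device. The log describes what participants record and does not explicitly order them to remove the wrist monitor. The MESA Sleep diary separately asks for removal times, which fits continuous wear. The hip entry in the MESA Sleep row is probably a labelling slip, since 6.2.6 describes no hip monitor. Central training, the requirement in 10.1.1 for identical conduct at all sites, and the day-3 call should also limit divergence. The log form and the detailed wear instructions are not in the protocol, so what participants are actually told cannot be seen. The hours that make a valid day are often left to a manual or analysis plan.

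Much of this stands, and it lowers the severity. It does not remove the conflict. The log's wording makes sense only if devices are exchanged, and Table 4 expressly permits sleep-only wear, so training to the protocol does not select one pattern.

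A reader might infer that 24-hour activity measures as a whole are lost. The documents do not support that, because hip and wrist records still combine to cover the day. Nor are naps lost: participants log them by clock time in the 24H-ACT log and again in the MESA Sleep diary.

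**Conclusion.** The inconsistency is real and should be fixed. For any participant who wears the wrist monitor only during sleep, 62.5% to 75% of the wrist record is missing (assuming 6 to 9 hours of sleep), and the wrist-based circadian rest-activity and daytime light measures planned for MESA Sleep cannot be derived. Full-day and sleep-only records could then be mixed in one data set, and the five-day repeat rule as written may not separate them. The 24H-ACT composite remains obtainable.

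It is tempting to go further and state how many MESA Sleep participants would be affected, or that wear will differ by site. The documents give no basis for either. They do not say what share would exchange devices, and the participant instructions are not shown. The conclusion concerns what the text permits, not how often it will happen.

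**What to change.** Reconcile 6.2.3, 6.2.6, Table 4 and the shared diary to one instruction that matches the main wrist sentence and MESA Sleep's purpose:

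- Wrist monitor worn 24 hours a day for the eight days; hip monitor worn in waking hours only.
- In the log, replace the exchange wording with times the hip monitor goes on and comes off and times of any wrist removal.
- Delete the sleeping-hours wording for the wrist monitor in 6.2.3 and the sleep-only alternative in Table 4.
- Correct the hip entry in Table 4's MESA Sleep row.
- Have the five-day wrist repeat rule count days with adequate 24-hour wear, with the threshold stated or referenced.

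The cost is revised wording in the protocol, log and participant instructions, plus the minor burden of two devices in the daytime. If some participants were already monitored before the change, their records should be classified by observed waking wrist wear before rhythm or light measures are computed.
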